treatment, is based on the premise that participants need to practice the skills in order to improve. Since participants commonly forget to do the skills, lose their homework assignments, or feel unmotivated to complete the skills, it challenges treatment developers to improve the current treatments and address these barriers to patient compliance. **We propose using a mobile app to improve patient compliance for youth at risk for SMD.** A mobile app can remind participants of skills they need to practice, provide the psychoeducation and skill-practice within the app, and provide contingencies that reward and increase motivation for skill-practice. Additionally, the large amounts of data that a mobile app collects allows for advanced statistical techniques, such as machine learning, to be applied. These efforts can provide a wide range of benefits to youth at risk for SMD and clinical science more broadly. Improving patient compliance can improve treatment outcomes, which reduces burdens on families who face these psychiatric challenges and society at-large who faces this emotional and financial burden. Additionally, through use of machine learning, we can better determine who will and who is benefitting from a skills-based treatment, like CBT. This prediction can help us better tailor treatment recommendations for patients and determine which patients will or will not benefit from a particular type of treatment.

STATISICAL DESIGN AND POWER

Power calculations

For this pilot RCT, we plan to randomize 60 participants to the randomized controlled-trial of the mobile-enhanced treatment. The two treatment groups will be randomized in a 1:1 ratio. Based on pilot trials of this treatment group as well as my primary mentor's ([name]) previous work with interventions for adolescents at high risk for SMI, we anticipate no more than 15-20% dropout by the end of the six-month study. Thus, we expect a final sample size of about 50 with full follow-up (25 in each treatment condition) across 3 assessment time-points (baseline, post-treatment, and three-month follow-up). Actual power will be higher as our general linear mixed modeling allows inclusion of data from subjects with partial data.

Additionally, data collected via the mobile application (app) should greatly increase the number of measurements.

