The power calculation assumes a two-sided significance level, $\alpha=.05$, and a within-subject correlation of $r=.5$ between repeated measures. Under these calculations, for outcomes measures at the three primary assessment time-points, we have 80% power to detect an overall group by time interaction corresponding to a differential treatment effect across the two study arms with an effect size of $f=.30$, just above the above Cohen's threshold for a medium effect ($f=.25$). Thus, recruiting 60 participants will provide ample data for this pilot RCT in order for us to determine initial clinical meaningfulness for the larger grant application to follow this study. However, in accordance with NIMH guidance on the role of pilot RCTs (see: <https://grants.nih.gov/grants/guide/rfa-files/RFA-MH-18-706.html>), this study does not propose to formally assess clinical efficacy or estimates of effect size, due to the unreliability of estimates and limited statistical power yielded from pilot studies.

Statistical analyses

Aim 1 – App acceptability:

- Open trial acceptability: Following the open-trial, we will score participants' rating of app acceptability and treatment satisfaction and burden. We expect high ratings of acceptability (scores>4/5) for the treatment and the app. We will also calculate participant adherence via the extent of weekly practice and percentage of weekly skills practiced. We expect the percentage of weekly skills practiced to be greater than our pilot study as well as the average homework adherence in the literature (>50%).

Aim 2 – Pilot RCT of App-UP:

- Primary Analyses: Treatment conditions will be compared using a general linear mixed modeling (GLMM) approach for the weekly measurements of treatment adherence (both self-report and clinician rated measures) using IBM SPSS software. Time will be based on the standard interval assessments of the study – the baseline, post-treatment, and follow-up assessment). Time, treatment condition, and their interaction will be the primary predictors (controlling for any significant covariates).

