The remaining measures for treatment adherence (i.e., Homework Compliance Scale and Psychosocial Compliance Scale), as well as measures for app acceptability (i.e., Subjective App Usability Scale) and treatment acceptability (i.e., Subjective Treatment Acceptability) will be collected at the post-treatment assessment. Maintenance of treatment adherence will also be collected at the 3-month follow-up assessment. Treatments will be compared on these outcome measures using one-way analysis of variance (ANOVA).

- **Secondary analyses:** Treatment conditions will be compared using a general linear mixed modeling (GLMM) approach for secondary outcome variables (i.e., psychiatric functioning and psychosocial functioning) using IBM SPSS software. Time will be based on the standard interval assessments of the study – the baseline, post-treatment, and follow-up assessment). Time, treatment condition, and their interaction will be the primary predictors (controlling for any significant covariates). Psychiatric symptoms, psychosocial functioning, and emotion regulation (measured continuously) will be the outcome variables for these analyses.

We will also test a mediation analysis, with average participant adherence (measured throughout the study) as the mediator between treatment conditions and the secondary outcome variables. This will be done in two sets of analyses using the SPSS Process macros, which is a statistical package within SPSS that runs bootstrapped mediation analyses. First, the effect of treatment condition, mediated by average treatment adherence, on post-treatment psychiatric and psychosocial functioning will be examined. Second, the effect of treatment condition, mediated by average treatment adherence, on 3-month follow-up psychiatric and psychosocial functioning will be examined.

- **Exploratory analyses:** Two exploratory analyses will be examined. We will make use of the app's big data collection to begin to elucidate the app's effect on participant adherence and clinical outcomes.

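### The secondary mixed models leave the baseline difference between arms free, which is valid but less efficient than adjusting for the baseline score already collected

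*Combined protocol and SAP*

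**What the plan says.** Under Statistical analyses, Aim 2, Secondary analyses, the arms are compared on psychiatric symptoms, psychosocial functioning and emotion regulation by a general linear mixed model in SPSS. Time has three levels, of which baseline is one. The fixed effects are given as "Time, treatment condition, and their interaction will be the primary predictors (controlling for any significant covariates"). The text names no baseline score as a covariate and does not constrain the arms to a common baseline mean.

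Under Power calculations the plan says "we plan to randomize 60 participants", 1:1, and expects about 50 with full follow-up, 25 per arm: "we anticipate no more than 15-20% dropout by the end of the six-month study". It assumes "a within-subject correlation of $r=.5$ between repeated measures" and a two-sided 5% level, and says "we have 80% power to detect an overall group by time interaction" at f = .30. The same section says that the pilot will not formally assess clinical efficacy or effect size.

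**The concern.** With time, treatment and their interaction in the model, the baseline difference between arms is a free parameter. Each interaction contrast is then a difference in change from baseline. Under randomisation the two baseline means are equal in expectation, so estimating them separately adds noise without removing any bias.

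At stake is the precision of the symptom and functioning estimates. With about 25 completers per arm they will be wide in any case, and the plan means to use the pilot to judge initial clinical meaningfulness for a larger application. The baseline score is collected anyway, so the lost precision could be recovered without more participants.

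**Working it through.** **The plan's own power figure.** The usual noncentrality for a within-between interaction is f²·N·m/(1−r) = 0.09 × 50 × 3 / 0.5 = 27, on 2 and 96 degrees of freedom. This gives 99.8% power, not 80%. Conventions that define the noncentrality differently give 44% to 91% at N = 50. The only variant tried that matched 80% was a one-degree-of-freedom test between arms at N = 60 (79.9%), which is not the interaction. The 80% is therefore not reproduced. That is a separate matter, and nothing below depends on it.

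**Inputs.** r = .5, 60 randomised 1:1 and about 25 completers per arm, from Power calculations; three visits, from Secondary analyses. Assumed: equal variances and one common correlation across visits (compound symmetry), and independent participants.

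**Visit contrasts, complete data.** Per-arm variance in units of the outcome variance; the variance of the arm contrast is this times 2/n.

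| Contrast | Baseline free | Baseline adjusted | Precision given up |
|---|---|---|---|
| Single later visit | 2(1−r) = 1.00 | 1−r² = 0.75 | 25% |
| Mean of two later visits | (1+r)/2 + 1 − 2r = 0.75 | (1+r)/2 − r² = 0.50 | 33% |

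- The standard error with adjustment is smaller by 1 − √0.75 = 13% and 1 − √(0.50/0.75) = 18%.
- Fifty completers in the planned model are worth 50 × 0.75 = 37.5, or 50 × 0.50/0.75 = 33.3, analysed with adjustment.
- The difference detectable at 80% power with 25 per arm (noncentral t, two-sided 5%) falls from 0.81 to 0.70 SD at a single visit and from 0.70 to 0.57 SD for the mean.
- In the covariate version the baseline slope must be estimated. At N = 50 this inflates the adjusted variance by about 1.022, leaving a loss of about 23% and 32%.

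**The plan's dropout.** Take 30 per arm at baseline and 25 complete, with dropouts contributing baseline only.
- Single visit: free 2 × (0.75/25 + 0.25/30) = 0.0767; adjusted 2 × 0.75/25 = 0.06; loss 22%.
- Mean of two: free 2 × (0.50/25 + 0.25/30) = 0.0567; adjusted 2 × 0.50/25 = 0.04; loss 29%.
- With 24 completers per arm the losses are 21% and 29%.

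**Other correlations.** For the change contrast with complete data, the loss is 35% and 47% at r = .3, and 15% and 20% at r = .7. If the planned model is read as the arm difference at the later visit rather than the change, the loss at r = .5 is the same. Away from .5 it differs: 9% and 14% at r = .3, and 49% and 58% at r = .7.

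**Therapy-group clustering.** The documents give no intraclass correlation. As an assumption, take 0.05 to 0.10, groups of six and a group effect constant over both later visits. This adds 5 × 0.05 = 0.25 to 5 × 0.10 = 0.50 to each per-arm variance.
- Single visit: 1.25 against 1.00 (20%) to 1.50 against 1.25 (17%).
- Mean of two: 1.00 against 0.75 (25%) to 1.25 against 1.00 (20%).

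**Overall two-degree-of-freedom interaction.** The per-arm covariance of the two later contrasts has variance 1.00 and covariance 0.50 when baseline is free, and 0.75 and 0.25 when adjusted. The noncentrality is proportional to δ′V⁻¹δ.

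| Effect at the two visits | Free | Adjusted | Loss |
|---|---|---|---|
| 1, 1 (sustained) | 1.333 | 2.000 | 33% |
| 1, 0.5 (halves) | 1.000 | 1.375 | 27% |
| 1, 0 (one visit only) | 1.333 | 1.500 | 11% |
| 1, −1 (equal and opposite) | 4.000 | 4.000 | 0% |

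**The case against.** The strongest reply is that the planned model is conventional and unbiased in a randomised trial, and that this choice does not inflate type I error. The outcomes are secondary and the plan disclaims formal efficacy testing, so no confirmatory decision rests on them. All of that stands and limits the weight of the point. It does not remove it: the plan still compares the arms on these outcomes, and its reason for the disclaimer, unreliable estimates and limited power, favours using the data efficiently.

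A reader might infer that the model discards 25-33% of the available precision as a fixed property, or that the trial needs a third to a half more participants. The documents do not support that. The power section targets the overall interaction, for which the loss depends on the shape of the effect and can be nil. The secondary analyses name neither a single-visit nor a two-visit-mean contrast. The 25% and 33% also need complete data, r = .5 and independent participants, whereas the plan expects dropout and treats participants in groups.

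It may also be said that the allowance for significant covariates already admits the baseline score. None is named there, selection would depend on the data, and baseline is already a response. Where the protocol does name covariates for its outcome analyses (extra counselling sessions and ancillary services), they are post-randomisation quantities.

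**Conclusion.** The point holds as an efficiency improvement to the secondary analyses. As written, those models leave the baseline arm difference free and so make less use of the baseline than they could. At r = .5, under compound symmetry, complete data and independent participants, the cost is a quarter of the precision at one visit and a third for the two-visit mean. The plan's dropout brings this down somewhat, and a higher correlation (for the change contrast) or clustering by therapy group brings it down further. For the overall interaction the loss is substantial only if the effect is sustained or partly sustained. The stronger reading, that the planned analysis is wrong or biased, is not supported.

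**What to change.** For the secondary outcomes, prespecify one of two models:

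- Keep baseline as a response but give both arms a common baseline mean: time plus treatment-by-time terms at post-treatment and follow-up only.
- Use post-treatment and follow-up as the responses, with the baseline score of the same measure as a fixed covariate, whether or not it is significant.

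Report the adjusted difference between arms with its confidence interval at each of the two visits.

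The cost is small: one or two sentences in the plan and a change of SPSS syntax, with no new data or participants. Two conditions should be written down. Baseline must be measured before allocation is known: the protocol reviews baseline assessments when deciding eligibility, but Overview of study activities does not say whether the pre-treatment assessment precedes randomisation. The covariate version also needs a rule for missing baseline scores, since otherwise those participants drop out of the analysis.

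### The mediator for post-treatment functioning is not limited to adherence recorded before that outcome, so reverse causation could be reported as mediation

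*Combined protocol and SAP*

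**What the plan says.** Under Statistical analyses, Aim 2, Secondary analyses, the plan names one mediator: "We will also test a mediation analysis, with average participant adherence (measured throughout the study) as the mediator between treatment conditions" and the secondary outcomes. It is then used twice. In the first analysis, "the effect of treatment condition, mediated by average treatment adherence, on post-treatment psychiatric and psychosocial functioning will be examined". The second reads: "Second, the effect of treatment condition, mediated by average treatment adherence, on 3-month follow-up psychiatric and psychosocial functioning will be examined". No averaging window is given for either.

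Four other places bear on how far the average reaches:

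- Overview of study activities puts the RCT's last assessment three months after the group ends.
- Power calculations and Addressing Clinical Emergencies both describe the RCT as lasting six months.
- The Aim 2 primary analyses add: "Maintenance of treatment adherence will also be collected at the 3-month follow-up assessment".
- The primary adherence model concerns weekly measurements, with no stated end date, and lists the follow-up among its time-points.

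**The concern.** Mediation requires the mediator to come before the outcome. Under Knowledge Gained, the protocol sets out its mechanism: the app raises skill practice, and practice improves outcome. This mediation is the plan's direct test of that chain.

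Youths who feel better at the end of the group may keep practising, or may stop because they no longer see the need. In either case the post-treatment outcome influences later adherence. If that later adherence is averaged into the mediator, mediator and outcome become correlated even when practice during treatment did nothing. Because the app is expected to raise adherence, the product of the two paths is then not zero. Bootstrapping the product does not restore the time order, and a larger sample would not remove the bias. The pilot is meant to inform a larger grant application, so a false mechanism signal could carry forward.

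**Working it through.** **Time order from the text.** The post-treatment outcome is measured when the group ends. The study continues for three more months, and adherence is collected at the end of them. An average over the whole study, taken literally, spans both sides of the outcome. No sentence cuts it off at post-treatment. The plan gives no power or effect size for the mediation, so there is no stated figure to reproduce.

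**Illustration of size.** From the documents: about 50 participants with full follow-up, 1:1 allocation, two-sided 5% level. Everything else is an assumption:

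- A1 is adherence during treatment, A2 adherence after it, and Y the post-treatment outcome, each with SD 1 within arm.
- A1 has no effect on Y, so the true indirect effect is 0.
- A2 = .5 × A1 (net of arm) + ρ × Y + error. There is no direct arm effect on Y.
- The mediator is M = (1−w) × A1 + w × A2, where w is the follow-up share.

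Three possible values of w, taking the nine sessions as weekly:

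- Nine weekly values plus one follow-up value: 1/10 = 10%.
- One post-treatment and one 3-month score: 1/2 = 50%.
- Weekly records through both periods: 13/(9+13) = 59%.

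Within arm, Cov(M,Y) = w × ρ and Var(M) = (1−w)² + w² + 2w(1−w) × .5. The false indirect effect is a × wρ / Var(M), where a is the arm effect on M.

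Worked case, w = .5, ρ = .3, a = 0.8: Cov = .15; Var = .25 + .25 + .25 = .75; slope = .15/.75 = .20; indirect effect = 0.8 × .20 = 0.16 outcome SD, against a true 0.

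The false-positive rates come from simulations of 2,000 trials per setting, with a Monte Carlo 95% interval for the product standing in for the bootstrap. Ranges show the spread between repeated runs. Each cell gives the false indirect effect (outcome SD), then the false-positive rate.

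| App effect on adherence; path ρ | w = 10% | w = 50% | w = 59% |
|---|---|---|---|
| 0.8 SD; .4 | 0.04; 5–6% | 0.21; 32–33% | 0.25; 41–43% |
| 0.8 SD; .3 | 0.03; 4–6% | 0.16; 20–21% | 0.19; 26–28% |
| 0.8 SD; .1 | 0.01; 4% | 0.05; 6–7% | 0.06; 6–7% |
| 0.5 SD during, 0.3 SD after; .3 | 0.02; 2% | 0.08; 7% | 0.09; 9% |
| 0.3 SD; .3 | 0.01; 1% | 0.06; 6% | 0.07; 6% |

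With w = 0 and a 0.8 SD app effect the rate is about 4%. With ρ = 0 it is 3–5% at every share.

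A second set of assumed values points the same way: app effect 0.6 SD on in-treatment adherence, path .3–.5, share 25–50%. The mean false indirect effect was 0.05–0.15 and 4–21% of intervals excluded 0. With the mediator restricted to the treatment period, the mean was about 0.00 and the rate 2–3%.

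**The case against.** The strongest reply is that the average was never meant to include follow-up. The follow-up measure has its own label, maintenance of adherence, and its own ANOVA comparison, and no sentence says it enters the mediator. On that reading the mediator is the average of the weekly values over the nine sessions, and the time order is sound. This is plausible. A reader might infer that the plan definitely places post-outcome data in the mediator, and the documents do not support that. What stands is that the wording permits it, and that an analyst following the text literally would include those data.

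A second reply concerns size. A reader might take 20–43% as the expected error rate. The 59% share needs weekly records to continue for 13 weeks after the group, which no section states. It also needs such records in the arm without the app. The 50% share leaves out the weekly measurements. The 10% share fits the documented follow-up collection best, and there the inflation is negligible. The 0.8 SD app effect and the paths of .3–.4 are not in the documents either. This reply stands in full as a limit on the size.

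A reader might also infer that the 3-month mediation is equally faulty. It is not. Practice after the group can precede the 3-month outcome and be a real part of the mechanism. Adherence collected at the same visit as the outcome weakens the time order but does not reverse it.

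Finally, this is a secondary analysis in a pilot that disclaims formal efficacy testing, and the primary adherence comparison is unaffected. That lowers the stakes but does not justify leaving the window open.

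**Conclusion.** The concern holds in a limited form. The averaging window is open-ended and, read literally, lets adherence recorded after the post-treatment outcome into the mediator for that outcome. The direction of the problem follows from the text. Its size does not.

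At N=50 with no true mediation, there is no material inflation above the nominal 5% (about 1–7%) in any one of three cases: the follow-up share is 10%, the app effect is 0.3 SD at path .3, or the path is .1. At 0.3 SD the rate does rise, from about 1% at a 10% share to about 6% at the larger shares, but it stays near nominal. The rate reaches about 20–43% only when the share is 50–59%, the app effect is 0.8 SD and the path is .3–.4 together. If the post-treatment outcome does not influence later adherence, there is no bias.

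The correction is worth making because it is nearly free and removes a choice of window that could otherwise be made after the data are seen.

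**What to change.** For the post-treatment mediation, replace the throughout-the-study wording with a mediator that covers the treatment period only: the weekly adherence values over the nine sessions, plus the Homework Compliance Scale and Psychosocial Compliance Scale collected at post-treatment if they are part of the average. Exclude anything recorded after the post-treatment assessment. Ending the window at the ninth session would needlessly drop those two scales, so the cut-off should be the post-treatment assessment itself.

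For the 3-month mediation, state which adherence data enter the average. If follow-up adherence is included, the in-treatment average can be reported as a sensitivity analysis. Requiring the in-treatment average there as the main analysis would leave practice after the group uncredited, so that is a trade-off for the investigators to settle in advance.

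The cost is a sentence or two in the analysis plan, using data already collected. The downside is that slightly fewer adherence data enter the post-treatment mediator.

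### The mediation analysis names no baseline-outcome covariate, so any link between baseline severity and adherence biases the indirect effect, in a direction the documents do not settle

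*Combined protocol and SAP*

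**What the plan says.** The mediation is described in the combined protocol and SAP under Statistical analyses, Aim 2, Secondary analyses. It is a bootstrapped model in the SPSS PROCESS macro, "with average participant adherence (measured throughout the study) as the mediator between treatment conditions and the secondary outcome variables". It is run twice, each time on an outcome at a single time point. For the end of treatment the wording is "First, the effect of treatment condition, mediated by average treatment adherence, on post-treatment psychiatric and psychosocial functioning will be examined". A parallel sentence repeats the same model with the outcome taken at the 3-month visit instead.

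The paragraph names no covariate. The baseline values exist: the power section counts on data "across 3 assessment time-points (baseline, post-treatment, and three-month follow-up", and the secondary mixed models use baseline as one of their time points. Of those models the plan says "Psychiatric symptoms, psychosocial functioning, and emotion regulation (measured continuously) will be the outcome variables for these analyses".

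Covariates are mentioned elsewhere, but none of the mentions supplies the baseline outcome here:

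- For the primary and secondary mixed models: "Time, treatment condition, and their interaction will be the primary predictors (controlling for any significant covariates". This does not name the baseline outcome and is not repeated for the mediation.
- Limits to Confidentiality: extra counselling sessions are to be covariates. These occur after randomisation.
- Availability of Other Ancillary Treatments: use of non-protocol services is to be a covariate. This too is recorded during the study.

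**The concern.** Arm is randomised; adherence is not. Under Knowledge Gained the protocol itself says that participants "lose their homework assignments, or feel unmotivated to complete the skills". The step from adherence to outcome is therefore an observational comparison. A characteristic that precedes treatment and predicts both adherence and outcome will bias it, and baseline severity is the obvious candidate. In the mixed models baseline enters as a time point. In the mediation, with its single-time outcome, it drops out altogether.

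The documents do not say whether more severe youths practise more or less. If they practise less, leaving out baseline creates or inflates an apparent benefit of adherence. If they practise more, it creates an apparent harm or hides a true benefit.

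The analysis matters because it is the plan's mediation test of the idea that CBT "is based on the premise that participants need to practice the skills in order to improve", and the pilot is meant to inform a larger application.

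**Working it through.** **Inputs from the plan.** The plan gives no figure for the mediation; its 80% power refers to the group-by-time interaction and is not used here. Power calculations gives 60 randomised 1:1, 15-20% dropout, about 50 completers (25 per arm), and r = .5 between repeated measures. The completer number is consistent: 60 × 0.85 = 51 and 60 × 0.80 = 48.

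**Assumed inputs.** The documents give no value for the app effect on adherence (a), the slope of adherence on baseline (g), or the true adherence-outcome slope (b). They are varied below.

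**Model.** Within-arm SD units, higher outcome = worse, T = arm, B = baseline, M = adherence, Y = outcome, no direct effect of T:

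- M = a·T + g·B + error
- Y = b·M + 0.5·B + error

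**Formula.** B is independent of T by randomisation, and B and M have unit within-arm SD, so the within-arm slope of B on M is g. With B omitted, the slope of Y on M is b + 0.5·g. The indirect effect becomes a·(b + 0.5·g), and its bias is 0.5·a·g. The total effect of arm is not biased; the error moves between the indirect and direct parts.

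**Simulation.** 3,000 trials per setting at n = 50, with 1,000 percentile-bootstrap resamples each. The Monte Carlo standard error is about 0.5 points at 9% and 0.9 points at 40%.

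*No true adherence effect (b = 0; true indirect effect 0):*

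| a | g | 0.5·a·g | Simulated, unadjusted | Interval excludes 0, unadjusted | Interval excludes 0, adjusted |
|---|---|---|---|---|---|
| 0.4 | -.2 | -0.04 | -0.041 | 2.6% | 1.2% |
| 0.4 | -.4 | -0.08 | -0.078 | 6.8% | 1.0% |
| 0.4 | +.2 | +0.04 | +0.039 | 2.9% | 1.3% |
| 0.4 | +.4 | +0.08 | +0.079 | 7.5% | 1.9% |
| 0.6 | -.3 | -0.09 | -0.092 | 10.4% | 3.6% |
| 0.6 | 0 | 0 | 0.000 | 3.0% | 3.4% |
| 0.6 | +.3 | +0.09 | +0.094 | 10.5% | 3.0% |
| 0.8 | -.2 | -0.08 | -0.079 | 8.6% | 4.7% |
| 0.8 | -.4 | -0.16 | -0.164 | 23.3% | 5.2% |
| 0.8 | +.2 | +0.08 | +0.076 | 8.4% | 4.6% |
| 0.8 | +.4 | +0.16 | +0.154 | 20.7% | 4.4% |

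With baseline adjusted, the mean indirect effect lies within 0.005 SD of zero in every row.

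*True benefit (b = -.3, a = 0.6; true indirect effect 0.6 × -.3 = -0.18):*

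| g | 0.6·(-.3 + 0.5·g) | Simulated, unadjusted | Benefit shown, unadjusted | Simulated, adjusted | Benefit shown, adjusted |
|---|---|---|---|---|---|
| -.3 | -0.27 | -0.272 | 51.4% | -0.181 | 39.5% |
| 0 | -0.18 | -0.183 | 30.8% | -0.183 | 37.6% |
| +.2 | -0.12 | -0.123 | 16.1% | -0.181 | 35.0% |
| +.3 | -0.09 | -0.087 | 8.4% | -0.177 | 32.9% |
| +.4 | -0.06 | -0.060 | 5.4% | -0.180 | 31.7% |

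A repeat run of the g = +.3 row gave 10.3% against 34.3%. If the total baseline-outcome correlation is held at .5, instead of the direct slope, that row gives -0.076 and 7.7%, against 36.3% adjusted.

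**Averaging window.** The mediator's wording could include adherence recorded at the 3-month visit, after the post-treatment outcome. One such value averaged with nine session values has a weight of 1/10. With a further assumed model for late adherence (0.5·M - 0.3·Y + error; a = 0.6, b = 0, g = 0), the shift is -0.019 SD and the interval excludes zero in 3.4% of trials. That is negligible.

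**The case against.** The strongest reply is that the harm rests on a relation the documents do not supply. Forgetting, lost homework and low motivation are not tied to severity anywhere. With g = 0 there is no bias, and at |g| = .1 with a = 0.6 and b = 0 the interval excludes zero in 3.3% of trials whether or not baseline is adjusted. At the weakest inputs tabulated, the unadjusted rate is below the nominal 5%. Rates above 20% need a = 0.8 together with |g| = .4. All of this is right, and it is why the point is conditional.

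Second, the plan is silent rather than committed to an unadjusted model, and its covariate clause for the mixed models might be meant to carry over. Even so, that clause does not name baseline, and it would leave inclusion to a significance test at about n = 50.

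Third, little depends on the result. It is secondary, and the pilot disclaims formal assessment of efficacy. When a true effect is assumed, even the adjusted analysis finds it in only 32% to 40% of trials. Motivation is a separate confounder that baseline severity need not capture. This limits the weight of the point. It does not favour leaving out baseline, since adjustment raises detection even at g = 0.

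**Conclusion.** The concern holds, conditionally and with modest weight. Bias in the indirect effect needs three things: baseline predicts outcome (the plan's r = .5 supports this), the app changes adherence (the trial's premise), and baseline severity is related to adherence (unknown).

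For the assumed a of 0.4 to 0.8 SD and |g| of .2 to .4, with no true adherence effect, the spurious indirect effect is 0.04 to 0.16 SD in either direction. The interval excludes zero in 2.6% to 23.3% of trials, against 1.0% to 5.2% adjusted. Where a true benefit of -0.18 SD exists, the omission can halve it or inflate it by half. The primary adherence comparison and the total effect of arm on outcome are unaffected. The averaging window is a matter of clarification only and adds no weight.

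**What to change.** State in the SAP that the baseline value of each outcome is a covariate in both the mediator equation and the outcome equation.

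Add one clarifying line: for each outcome, the average uses only adherence recorded before that assessment, and the measures that form it are named (for example, the weekly self-report and clinician ratings used in the primary analysis). Using the on-treatment mean for the 3-month outcome as well is optional.

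Report the mediation as hypothesis-generating, because confounding by motivation and other common causes remains after this change.

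The cost is two or three lines of wording and one degree of freedom per equation. The baseline outcomes and weekly adherence are already collected.
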